6.1.6 Study drug packaging and labeling

The vials will be packaged and labeled in local language according to Good Manufacturing Practice and national regulations/guidelines, specifying that the drug is for use in a clinical trial.

6.1.7 Study drug management

6.1.7.1 *Accountability*

Study drug sent to the partially unblinded pharmacist (or other qualified personnel) at the investigational site will be accounted for and no unauthorized use is permitted. The designed personnel will acknowledge receipt of the study drug using IRT to confirm the shipment condition and content. If a damaged shipment is received, he/she will notify the Sponsor/ CRO, quarantine the shipment in a specific storage area, and document the event as specified in the pharmacy manual.

The designed personnel will also maintain accurate records of the study drug throughout the clinical trial, including the inventory delivered to the site, the use by each subject, the reconciliation of all delivered and received vials of study drug, and the return of used and unused study drug as specified in the pharmacy manual.

6.1.7.2 *Storage of study drug*

All vials of study drug must be stored together in a safe and secure area with restricted access. Upon receipt, the study drug must be removed from the shipping cooler, stored in a refrigerator between 2 and 8°C (36-46°F) and protected from light. The refrigerator must be monitored daily, and if temperature excursion occurs, the designed personnel should promptly inform the partially unblinded Clinical Research Associate (CRA) as specified in the pharmacy manual.

6.1.7.3 *Dispensing and return*

All drug preparation must be appropriately performed and documented by the designated personnel (partially unblinded pharmacist or other qualified personnel). Any error in the preparation of dosing solution must be reported to the partially unblinded CRA promptly and properly documented. At the end of the study, all unused study drug will be returned to the CRO/drug depot for destruction.

6.1.7.4 *Treatment compliance management and record*

Treatment compliance will be assessed through the drug dispensation and accountability logs.

6.1.8 Dose modification and study drug discontinuation

6.1.8.1 Dose modification

Dose modification of the study drug will not be permitted throughout the clinical trial. Any inadvertent dose modifications should be discussed with Sponsor/CRO.

6.1.8.2 Study drug discontinuation

The study drug must be permanently discontinued when any of the following conditions is reported for a subject during the clinical trial:

- Serious immediate-type allergic manifestations including anaphylactic reaction
- Diagnosis of a malignancy (except curatively treated in situ cervical carcinoma or basal cell carcinoma)
- Pregnancy
- Any opportunistic infection (such as active TB and other infections whose nature or course suggest an immune-compromised status)
- Systemic rescue therapy (such as cyclosporine, systemic corticosteroids, methotrexate, mycophenolate mofetil, azathioprine or biologics) or TCI used in body areas other than the face, neck, or genital areas
- Asthma /worsening of asthma reported as a serious adverse event

In the event that the study drug is discontinued, the subjects should remain in the study and will be asked to return for all remaining visits and all assessments (including daily assessments of pruritus and sleep disturbance) according to, except those who withdraw their consent for study participation.

In the event of a missed dose (i.e. temporary discontinuation of the study drug), it will be documented in the eCRF that the drug has not been administered at the study visit, together with the reason (e.g. for safety reason). Subjects will be asked to return to the investigational sites for all remaining visits and complete all study assessments and procedures as described in [Table 2](#).

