The medium potency TCS will not exceed an amount of approximately 100 g/month (Eichenfield 2015) and the low potency an amount of approximately 30 g/month. The TCS regimen will be adjusted during the study, according to the disease activity and tolerability by the subject: where lesions are cleared, TCS should be applied at a reduced frequency (e.g. from every other day to twice weekly) and then discontinued; they can also be applied at a reduced frequency or discontinued if judged to be medically necessary by the investigator (e.g. due to intolerance).

5.3.4.2 *Rescue therapies*

If deemed to be medically necessary by the investigator (i.e. significant worsening of signs and/or symptoms of AD), rescue therapies can be prescribed to the subjects at any time during the study. For the purpose of efficacy analysis, subjects receiving any rescue therapies will be considered as treatment failures. Whenever possible, efficacy and safety assessments (e.g. disease severity scores, laboratory tests) should be conducted immediately before administering any rescue therapies.

Rescue therapies could include higher potency and/or quantity of TCS, TCI, systemic treatment, phototherapy or combinational usage of different treatment modalities. Whenever possible, investigators should first use topical medications as rescue therapy, before escalating to systemic therapies. If subjects receive topical treatments or phototherapy as rescue therapy, study drug administration should be continued unless there is a safety concern according to the investigator's judgment (e.g. TCI are applied in large body areas other than the face, neck, or genital areas). If subjects receive a systemic rescue therapy (such as cyclosporine, systemic corticosteroids, methotrexate, mycophenolate mofetil, azathioprine or biologics) or TCI in large body areas, the study drug administration must be permanently discontinued (see Section 6.1.8.2).

Whenever possible, subjects should complete all study visits and assessments (including daily diaries), regardless of whether or not they have received rescue therapies and whether or not they have discontinued the study drug administration.

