7.2.5.2.4 Procedures for reporting pregnancies

Any pregnancy occurring during clinical trials, where the fetus could have been exposed to the study drug, must be monitored until its outcome in order to ensure the complete collection of safety data.

If a subject becomes pregnant, the investigator must:

1. **Withdraw the subject from the clinical trial. The subject must not receive any further injection of the study drug.**
2. Complete as fully as possible the Pregnancy Surveillance Form – Part I: History and Start of Pregnancy, available in the eCRF. Print and send it by e-mail along with the exit form **within 24 hours** of receipt of the information, to the GMS within the CRO (contact see Section [7.2.5.2.2](#)). (*Of note, in case there is no access to the eCRF, please refer to the instructions in the Investigator Site File for reporting a pregnancy*).
3. Monitor and record the progress of the pregnancy until its outcome. Contact the subject's regular physician (general practitioner or gynecologist) or hospital staff to obtain further details and ask for regular follow-up information.
4. Provide tri-monthly updates until the final outcome of the pregnancy, by completing the Pregnancy Surveillance Form – Part II: Course and Outcome of Pregnancy. For all these additional follow-up evaluations, print and send the form by e-mail to the GMS within the CRO **within 24 hours** of receipt of the information. If the subject can no longer be reached (lost to follow-up), documentation of the non-response/contact with two phone calls and a letter (certified with return receipt) is required.
5. At the outcome of the pregnancy, complete as fully as possible the Pregnancy Surveillance Form – Part II: Course and Outcome of Pregnancy. Print and send the form by e-mail to the GMS within the CRO **within 24 hours** of receipt of the information.
6. If the pregnancy leads to an abortion (voluntary abortion, spontaneous abortion or therapeutic abortion), *in utero* death or congenital anomaly, follow the procedure for declaration of an SAE (see Section [7.2.5.2.2](#)).

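### The mandatory TCI stopping rule is set by extent in Protocol 5.3.4.2 but by body site in 6.1.8.2, and the sections disagree on whether a pregnant subject leaves the study

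*Protocol*

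**What the plan says.** **TCI rescue.** Protocol 5.3.4.2 deals with it in two consecutive sentences, and the synopsis carries the same text. The first says that after topical rescue or phototherapy "study drug administration should be continued unless there is a safety concern" in the investigator's judgment, and gives as an example of such a concern that "TCI are applied in large body areas other than the face, neck, or genital areas". The second covers systemic rescue "or TCI in large body areas, the study drug administration must be permanently discontinued". In 5.3.4.2 this second sentence ends with a cross-reference to 6.1.8.2.

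Section 6.1.8.2 opens its list with "The study drug must be permanently discontinued when any of the following conditions is reported for a subject during the clinical trial". The rescue item in that list pairs systemic therapy with "TCI used in body areas other than the face, neck, or genital areas". The word *large* does not appear there.

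**Pregnancy.** The same list in 6.1.8.2 includes pregnancy. The text below it reads "In the event that the study drug is discontinued, the subjects should remain in the study" and asks for attendance at all later visits, with withdrawal of consent as the only exception. Section 8.1.4.1 repeats the rule without a pregnancy exception. Section 7.2.5.2.4 instructs the investigator: "Withdraw the subject from the clinical trial". It bars further injections in a separate sentence and calls for the exit form. Section 5.4 names pregnancy among the reasons for leaving the study, and it opens by distinguishing leaving the study from stopping treatment only.

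**Analysis.** SAP 4.7.1.3 sets efficacy data to missing once rescue is used, except in the observed-case (OC) analysis. The SAP does not restate or resolve either stopping rule.

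**The concern.** Both rules are instructions on subject management at about 70 sites. TCI is a named rescue option, and topical rescue is to be tried before systemic rescue where possible, so the TCI rule is likely to be needed. Where two sections state different mandatory triggers, two investigators can each follow the protocol and treat like subjects differently: one keeps injecting and the other stops for good.

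That would put noise that comes from the text, not from the drug, into exposure, discontinuation counts and any safety comparison on or off drug. For pregnancy, the question is whether visits after the event, including the week 24 primary assessment, are part of the planned data.

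**Working it through.** No figure in the plan depends on these rules, so the check sets the texts side by side and then follows each difference into the analysis.

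**Step 1: apply each TCI wording to four cases.**

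| TCI use | 5.3.4.2 and synopsis, judgment sentence | 5.3.4.2 and synopsis, mandatory sentence | 6.1.8.2 |
|---|---|---|---|
| Small area, outside face/neck/genitals | Continue by default | Not triggered | Must stop |
| Large area, outside face/neck/genitals | Investigator's judgment | Must stop | Must stop |
| Large area, within face/neck/genitals | Continue by default | Must stop, read literally | Not triggered |
| Small area, within face/neck/genitals | Continue by default | Not triggered | Not triggered |

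The two mandatory rules conflict in row 1 on any reading. They conflict in row 3 only if the mandatory sentence is not taken to inherit the site exemption from the sentence before it. In row 2 they agree; the only tension there is that the judgment sentence presents as discretionary what the next sentence requires. Row 4 is consistent throughout.

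**Step 2: apply each pregnancy wording to two questions.**

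| Question | 6.1.8.2 and 8.1.4.1 | 7.2.5.2.4 and 5.4 |
|---|---|---|
| Does study drug stop? | Yes | Yes |
| Does the subject stay in the study? | Yes, for all later visits | 7.2.5.2.4: no, withdrawn; 5.4: listed as a reason for leaving |

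The conflict is about study participation only.

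**Step 3: follow the TCI difference into the analysis.** Efficacy data after rescue become missing whether or not injections continue (SAP 4.7.1.3), so a TCI-rescued subject enters the primary repeated-measures model in the same way under either rule. What does change:

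- Counts of, reasons for and time to permanent treatment discontinuation (SAP 4.3.1).
- Cumulative dose and number of administrations (SAP 4.8.1).
- Injection compliance (SAP 4.6), defined as actual injections / planned injections × 100, with 80% to 120% counted as compliant. Day 1 plus weeks 4, 8, 12, 16 and 20 makes 1 + 5 = 6 planned injections. Stopping after five gives 5/6 = 83%, which is compliant; stopping after four gives 4/6 = 67%, which is not. This assumes that all six still count as planned after a required stop, which the SAP does not say.
- Adverse events, drug concentrations and anti-drug antibodies, which would be observed on or off drug.
- The OC sensitivity analysis, which keeps data after rescue.

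**Step 4: follow the pregnancy difference into the analysis.** Without rescue, no rule sets later efficacy data to missing merely because drug was stopped. If the subject stays, her week 24 EASI enters the primary model. If she is withdrawn before week 24, that value is missing unless her early termination visit falls on days 156 to 183, the week 24 window in SAP 4.2. On binary endpoints she counts as a non-responder after withdrawal (SAP 4.7.1.3).

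**The case against.** The best defence is that the TCI text can be read as one rule. The two sentences in 5.3.4.2 are adjacent: the first introduces a concern and the second states its consequence. The example in the first already carries the site exemption found in 6.1.8.2, and the cross-reference sends the reader to the stopping list. On that reading the main difference left is the word *large*. This largely answers the tension between judgment and requirement, and it may answer row 3. It does not answer row 1, where no reading satisfies both sections.

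On pregnancy, 7.2.5.2.4 is the event-specific procedure and the contrary text is a general rule, so a site may well follow the specific one. But the general rule names a single exception, and it is not pregnancy, although pregnancy stands in the list directly above it.

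A reader might also infer four stronger things that the documents do not support:

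- *Every subject given TCI outside the named sites is affected.* For large areas outside those sites both mandatory rules say stop.
- *Per-protocol membership turns on the conflict.* SAP Appendix 5 lists treatment administration errors, so an effect is possible. But permanent discontinuation is not itself listed, TCI authorised as rescue is exempt from the prohibited therapies (Protocol 5.3.5), and SAP 4.3.1 counts study treatment as completed when the week 24 visit is completed. Classification is settled in blinded review under a deviation specification that is not among the documents.
- *The TCI conflict alters the primary analysis of rescued subjects.* The rule on data after rescue prevents that.
- *Safety follow-up is lost after a pregnancy.* A subject withdrawn before week 24 is still asked to attend an early termination visit and a final visit 12 weeks after the last injection (5.4), and the pregnancy is followed to its outcome (7.2.5.2.4).

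**Conclusion.** Two contradictions stand. The mandatory TCI trigger is defined by extent in the synopsis and 5.3.4.2 and by site in 6.1.8.2. The instructions are opposite for small-area use outside the face, neck and genitals and, on a literal reading, for large-area use within those sites. A pregnant subject is kept in the study by 6.1.8.2 and 8.1.4.1 and withdrawn from it by 7.2.5.2.4, with 5.4 in support of withdrawal.

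The size is modest. The documents give no expected number of TCI rescues or pregnancies; both affected groups are probably small, which is a judgment and not a figure from the plan. The TCI conflict bears mainly on exposure and compliance, discontinuation counts, safety, PK and antibody data, the OC analysis and possibly deviation classification. The pregnancy conflict can reach efficacy data, since it decides whether later visits are collected or missing, but for few subjects. The contradictions are certain from the text. How often sites would in fact act differently is not known.

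**What to change.** Reconcile the synopsis, 5.3.4.2 and 6.1.8.2 into one TCI criterion, stated in the same words in each place. If extent remains part of it, say what counts as large, because these sections give no threshold. Make clear in the same text whether the judgment sentence in 5.3.4.2 still applies to TCI.

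Reconcile 5.4, 6.1.8.2, 7.2.5.2.4 and 8.1.4.1 into one instruction on whether a pregnant subject remains in the study and which visits she attends.

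Classify protocol deviations against the reconciled text. Which rule is right in each case is a clinical decision for the sponsor's team and is not proposed here.

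The cost is wording only, in an amendment or a clarification letter to sites. Neither the sample size nor the planned models change.

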6.2 Blinding

6.2.1 Verification of blinding

This is a double-blind clinical trial. With the exception of the partially unblinded pharmacist (or other qualified personnel) who will handle study drug preparation, the partially unblinded CRA who will monitor the drug records only, the unblinded statistician from the CRO

responsible for providing information to the IDMC and for the primary analysis, and the provisions in section 6.2.2, this study will remain blinded to all study individuals until the pre-specified unblinding at the end of the study.

All study personnel must follow the procedures described below to avoid compromising the blinding:

1. The randomization list will be managed through the IRT system with restricted access to designated personnel only;
2. Study drug management and preparation (including reconstitution and dilution) will be performed by the partially unblinded pharmacist (or other qualified personnel) only, while the evaluator will have no contact with the study drug. The person who will administer the study drug will receive only a syringe filled with 1.0ml of dosing solution ready for injection;
3. The partially unblinded pharmacist (or other qualified personnel) will be instructed to not discuss the study drug with the investigator/evaluator, the subjects or with the blinded CRA involved in the monitoring of study data;
4. A partially unblinded CRA will be responsible for monitoring the record of study drug only, and will have no access to other data collected during the study or to the eCRF. The partially unblinded CRA will also be instructed to not discuss trial-related matters with the investigator/evaluators, the subjects or with the blinded CRA involved in the monitoring of study data

6.2.2 Unblinding during the clinical trial

Emergency unblinding during the clinical trial may be required for therapeutic or for regulatory reasons (e.g. for expedited safety reporting). If unblinding is necessary, the investigator should unblind the study treatment for the specific subject only. If possible, the investigator should discuss with the CRO before breaking the blind. If not possible to discuss before, investigator must document the date, time and reason for the unblinding and notify the Clinical Safety Officer (CSO) from the CRO (contact details in Section 7.2.5.2.2) immediately afterwards.

The IDMC will review data blinded by treatment group during the study, but may request unblinding if necessary. Similarly, the IDMC will unblind the study treatment for specific subject(s) only.

6.3 Other supplies

Syringes, needles, water for injection, peak flow meters, D-squames, and urine pregnancy tests (UPTs, with a sensitivity < 25IU/L) will be provided to the investigational sites to be used in this clinical trial.

TCS of medium potency (mometasone furoate 0.1% cream or hydrocortisone butyrate 0.1% cream) and low potency (hydrocortisone acetate cream or desonide 0.05% cream) will be provided to the investigational site for dispensation to subjects as background TCS therapy in this clinical trial. Subjects (including screen failure subjects) will be instructed to bring the used and unused TCS tubes back to the investigational sites at each visit. TCS returned by the randomized subjects will be weighted first, and destroyed by the sites after monitoring. All other returned TCS will be destroyed by the sites after monitoring.

7 CLINICAL TRIAL ASSESSMENT

7.1 Efficacy assessments

7.1.1 Efficacy measurements

Efficacy measurements should be conducted by the investigators (or trained designees) and subjects (for patient-reported efficacy measurements) according to [Table 2](#). Whenever possible, the same evaluator should make the assessment throughout the study.

7.1.1.1 *Eczema Area and Severity Index (EASI)*

EASI is a composite score ranging from 0 to 72 ([Hanifin 2001](#), see [APPENDIX 2](#)). The severity of erythema, induration/papulation, excoriation, and lichenification will be assessed by the investigator or trained designee on a scale of 0 (absent) to 3 (severe) for each of the 4 body areas: head/neck, trunk, upper limbs, and lower limbs, with half points allowed. In addition, the extent of AD involvement in each of the 4 body areas will be assessed as a percentage by body area of head, trunk, upper limbs and lower limbs, and converted to a score of 0 to 6. The EASI score will be calculated in the eCRF.

7.1.1.2 *Investigator's Global Assessment (IGA)*

IGA is a 5-point scale ranging from 0 (clear) to 4 (severe) used by the investigator or trained designee to evaluate the global severity of AD ([Paller 2016](#); see [APPENDIX 3](#)).

7.1.1.3 *Body Surface Area (BSA)*

The BSA involvement of AD will be assessed by the investigator or trained designee for each part of the body (the possible highest score for each region is: head and neck [9%], anterior trunk [18%], back [18%], upper limbs [18%], lower limbs [36%], and genitals [1%]), and will be reported as a percentage of all major body sections combined.

7.1.1.4 SCORing Atopic Dermatitis (SCORAD)

SCORAD ranges from 0 to 103 and has three components: extent (BSA, as described in Section 7.1.1.3), signs and symptoms of AD (European task force on atopic dermatitis 1993, see APPENDIX 4). Investigator or designee will assess the severity of 6 signs of AD (erythema/darkening, edema/papulation, oozing/crusting, excoriation, lichenification/prurigo and dryness), each on a scale ranging from 0 (none) to 3 (severe). Investigator or designee will also ask the subjects to evaluate their symptoms of pruritus and sleep loss (average for the last 3 days/nights), each evaluated on a VAS from 0 to 10. The SCORAD score will be calculated in the eCRF.

7.1.1.5 Pruritus Numeric Rating Scale (NRS)

Pruritus NRS is a scale to be used by the subjects to report the intensity of their pruritus (itch) during the last 24 hours (see APPENDIX 5). Subjects will receive instructions on how to record their pruritus NRS scores on an electronic device, and will complete the assessment once daily in the evening throughout the clinical trial (including the run-in and the follow-up period).

Subjects will be asked the following questions in their local language:

- For average itch intensity: “On a scale of 0 to 10, with 0 being ‘no itch’ and 10 being ‘worst itch imaginable’, how would you rate your itch overall during the previous 24 hours?”
- For maximum itch intensity: “On a scale of 0 to 10, with 0 being ‘no itch’ and 10 being ‘worst itch imaginable’, how would you rate your itch at the worst moment during the previous 24 hours?”

